8.3.3. Clinical Safety Laboratory Assessments

Laboratory safety parameters will be graded according to the DAIDS Table for Grading the Severity of Adult and Pediatric Adverse Events[30], version 2.1. See [Appendix 2](#) for the list of clinical safety laboratory tests to be performed and the [SoA](#) for the timing and frequency. All protocol-required laboratory assessments, as defined in [Appendix 2](#), must be conducted in accordance with the laboratory manual and the [SoA](#). Unscheduled clinical laboratory measurements may be obtained at any time during the study to assess any perceived safety issues.

The investigator must review the laboratory report, document this review, and record any clinically significant changes occurring during the study in the AE section of the CRF. Clinically significant abnormal laboratory test findings are those that are not associated with the underlying disease, unless judged by the investigator to be more severe than expected for the participant's condition.

All laboratory tests with values considered clinically significant and abnormal during participation in the study or within 28 days after the last dose of study intervention should be repeated until the values return to normal or baseline or are no longer considered clinically significant by the investigator or study medical monitor.

If such values do not return to normal/baseline within a period of time judged reasonable by the investigator, the etiology should be identified and the sponsor notified.

See [Appendix 6](#) for suggested actions and follow-up assessments in the event of potential DILI.

See [Appendix 7](#) for instructions for laboratory testing to monitor kidney function and reporting laboratory test abnormalities.

8.3.3.1. Alternative Facilities for Clinical Safety Laboratory Assessment

If a local laboratory is used, qualified study site personnel must order, receive, and review results. Site staff must collect the local laboratory reference ranges and certifications/ accreditations for filing at the site. Laboratory test results are to be provided to the site staff as soon as possible. The local laboratory reports should be filed in the participant's source

documents/medical records. Relevant data from the local laboratory report should be recorded on the CRF.

8.3.4. Pregnancy Testing

A serum or urine pregnancy test is required at screening. Following screening, pregnancy tests may be urine or serum tests, and must have a sensitivity of at least 25 mIU/mL.

Pregnancy tests will be performed in WOCBP at the times listed in the [SoA](#). Pregnancy tests will also be done whenever 1 menstrual cycle is missed during the active treatment period (or when potential pregnancy is otherwise suspected) and at Day 34 or the ET visit. Pregnancy tests may also be repeated if requested by IRBs/ECs or if required by local regulations. If a urine test cannot be confirmed as negative (eg, an ambiguous result), a serum pregnancy test is required. In such cases, the participant must be excluded if the serum pregnancy result is positive.

For a female pediatric participant who becomes pregnant, this information will be shared with the study participant's parent/guardian if the participant's age is within the specific range based on local/country regulations.

8.3.4.1. At Home Pregnancy Testing

If a participant requiring pregnancy testing cannot visit a local laboratory, a home urine pregnancy testing kit with a sensitivity of at least 25 mIU/mL may be used by the participant to perform the test at home, if compliant with local regulatory requirements. The pregnancy test outcome should be documented in the participant's source documents/medical records and relevant data recorded on the CRF. Confirm that the participant is adhering to the contraception method(s) required in the protocol.

8.4. Adverse Events, Serious Adverse Events, and Other Safety Reporting

The definitions of an AE and an SAE can be found in [Appendix 3](#).

AEs may arise from symptoms or other complaints reported to the investigator by the participant (or, when appropriate, by a caregiver, surrogate, or the participant's legally authorized representative), or they may arise from clinical findings of the investigator or other healthcare providers (clinical signs, test results, etc).

The investigator and any qualified designees are responsible for detecting, documenting, and recording events that meet the definition of an AE or SAE and remain responsible to pursue and obtain adequate information both to determine the outcome and to assess whether the event meets the criteria for classification as an SAE or caused the participant to discontinue the study intervention (see [Section 7.1](#)).

During the active collection period as described in [Section 8.4.1](#), each participant/caregiver/parent/legal guardian/legally authorized representative will be questioned about the occurrence of AEs in a nonleading manner.

In addition, the investigator may be requested by Pfizer Safety to obtain specific follow-up information in an expedited fashion.

8.4.1. Time Period and Frequency for Collecting AE and SAE Information

The time period for actively eliciting and collecting AEs and SAEs (“active collection period”) for each participant begins from the time the participant provides informed consent, which is obtained before undergoing any study-related procedure and/or receiving study intervention, through and including a minimum of 28 calendar days, except as indicated below, after the last administration of the study intervention.

Follow-up by the investigator continues throughout the active collection period and until the AE or SAE or its sequelae resolve or stabilize at a level acceptable to the investigator.

When a clinically important AE remains ongoing at the end of the active collection period, follow-up by the investigator continues until the AE or SAE or its sequelae resolve or stabilize at a level acceptable to the investigator and Pfizer concurs with that assessment.

For participants who are screen failures, the active collection period ends when screen failure status is determined.

If the participant withdraws from the study and also withdraws consent for the collection of future information, the active collection period ends when consent is withdrawn.

If a participant permanently discontinues or temporarily discontinues study intervention because of an AE or SAE, the AE or SAE must be recorded on the CRF and the SAE reported using the PSSA.

Investigators are not obligated to actively seek information on AEs or SAEs after the participant has concluded study participation. However, if the investigator learns of any SAE, including a death, at any time after a participant has completed the study, and they consider the event to be reasonably related to the study intervention, the investigator must promptly report the SAE to Pfizer using the PSSA.

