1.2. Schema

1.3. Schedule of Activities

The SoA table provides an overview of the protocol visits and procedures. Refer to the **STUDY ASSESSMENTS AND PROCEDURES** section of the protocol for detailed information on each procedure and assessment required for compliance with the protocol.

The investigator may schedule visits (unplanned visits) in addition to those listed in the SoA table, in order to conduct evaluations or assessments required to protect the well-being of the participant.

Table 1. Study Schedule of Assessment

Visit Identifier	Screen	Treatment Period			Efficacy and Safety Follow-up Period					LTFU				Notes
Abbreviations used in this table may be found in Appendix 12 .		Baseline (Day 1)	Day 3	Day 5	Day 10	Day 15	Day 21	Day 28	Day 34	Week 12	Week 24	ET (prior to Day 34)		
 Day relative to start of study intervention (Day 1). Baseline (Day 1) visit is a mandatory visit. Assessments indicated in brackets [X] are only to be conducted if indicated as described in the “Notes”.
Visit Window	Day -1 to Day 1	0 days	±1 day	±1 day	±1 day	±2 days	±2 days	±2 days	±3 days	±7 days	±7 days	±5 days		
 Screening procedures may be done from Day -1 to Day 1 and may be completed on the same calendar day as Baseline/Day 1 procedures. If screening and baseline visits are conducted on the same calendar day, assessments and procedure that are listed to occur at both visits only need to be completed once.
Study Visit Location	S	S	S/P	S/P	S/P	S/P	S/P	S/P	S/P	T	T	S/P		
 Site staff should, in discussion with participants, determine the most appropriate location to conduct study visits. Visits should take place at the investigational site (S). If this is not feasible, then alternate venues may include the participant’s location (P). If an in-person visit is held at a location other than S, the HCP performing the visit may be unable to complete all assessments. In these cases, a telemedicine/telehealth visit should also occur to perform the remaining assessments.
ELIGIBILITY														

Table 1. Study Schedule of Assessment

Visit Identifier	Screen	Treatment Period			Efficacy and Safety Follow-up Period						LTFU		Notes	
		Baseline (Day 1)	Day 3	Day 5	Day 10	Day 15	Day 21	Day 28	Day 34	Week 12	Week 24	ET (prior to Day 34)		

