Study intervention dispensation		X												
 Study intervention will be dispensed on Day 1. (See Section 6.1.1) See Appendix 7 for age-specific kidney function calculations to determine nirmatrelvir dosing.
Study intervention administration		Days 1 through 5												
 Baseline assessments should be performed before administration of the first study intervention. The first dose of study intervention will be administered to all participants on Day 1 during the in-person visit. All subsequent doses of study intervention will be self-administered (or administered to the participant by a legal guardian or caregiver). If only 1 dose of study intervention is administered on Day 1, study intervention should end on Day 6. See Section 6.1.
Participant-completed study intervention log		Daily on Days 1 through 5												
 Participants will use a participant-completed electronic dosing diary to record the date and time of their study intervention dosing. Study intervention log should be completed daily on Days 1 through 6 if only 1 dose was administered on Day 1. See Section 6.5.

Table 1. Study Schedule of Assessment

Visit Identifier	Screen	Treatment Period				Efficacy and Safety Follow-up Period					LTFU			Notes	
		Baseline (Day 1)	Day 3	Day 5	Day 10	Day 15	Day 21	Day 28	Day 34	Week 12	Week 24	ET (prior to Day 34)			
Abbreviations used in this table may be found in Appendix 12 .														
 Day relative to start of study intervention (Day 1). Baseline (Day 1) visit is a mandatory visit. Assessments indicated in brackets [X] are only to be conducted if indicated as described in the “Notes”. 	
Visit Window	Day -1 to Day 1	0 days	±1 day	±1 day	±1 day	±2 days	±2 days	±2 days	±3 days	±7 days	±7 days	±5 days		
 Screening procedures may be done from Day -1 to Day 1 and may be completed on the same calendar day as Baseline/Day 1 procedures. If screening and baseline visits are conducted on the same calendar day, assessments and procedure that are listed to occur at both visits only need to be completed once. 	
Staff review of study intervention log		Daily on Days 1 through 5												
 Staff review of the study intervention log should be completed daily on Days 1 through 6 if only 1 dose was administered on Day 1. See Section 6. 	

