COVID-19 signs and symptoms										X	X			
 See Section 8.2.3.5.
Vital Status Check										X	X			
 Verify mortality status of participants.

Table 1. Study Schedule of Assessment

Visit Identifier	Screen	Treatment Period			Efficacy and Safety Follow-up Period						LTFU			Notes
		Baseline (Day 1)	Day 3	Day 5	Day 10	Day 15	Day 21	Day 28	Day 34	Week 12	Week 24	ET (prior to Day 34)		
Abbreviations used in this table may be found in Appendix 12 .														
 Day relative to start of study intervention (Day 1). Baseline (Day 1) visit is a mandatory visit. Assessments indicated in brackets [X] are only to be conducted if indicated as described in the “Notes”.
Visit Window	Day -1 to Day 1	0 days	±1 day	±1 day	±1 day	±2 days	±2 days	±2 days	±3 days	±7 days	±7 days	±5 days		
 Screening procedures may be done from Day -1 to Day 1 and may be completed on the same calendar day as Baseline/Day 1 procedures. If screening and baseline visits are conducted on the same calendar day, assessments and procedure that are listed to occur at both visits only need to be completed once.
Serious and nonserious AE monitoring	X	X	X	X	X	X	X	X	X			X		
 AEs should be assessed by means of a telemedicine visit if an in-person visit is not feasible. Previously identified AEs (either by interview, physical exam, or other assessment) should be monitored to the extent possible if telemedicine is used. See Section 8.4.3 for follow-up AE and SAE assessments.

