4. STUDY DESIGN

4.1. Overall Design

This Phase 2, randomized, double-blind, placebo-controlled study will evaluate the efficacy and safety of a repeat 5-day treatment course of nirmatrelvir/ritonavir or placebo/ritonavir for the treatment of mild-to-moderate COVID-19. Participants must have written documentation, such as an electronic health record, medical record, or prescription receipt of treatment with nirmatrelvir/ritonavir (verbal assertion of treatment is not acceptable) with patient-reported 100% compliance (ie, completed a 5 day course of nirmatrelvir/ritonavir). They must have experienced alleviation or resolution in COVID-19 signs/symptoms followed by a worsening (rebound) of signs/symptoms along with a positive rapid antigen test after completing an initial 5-day course of nirmatrelvir/ritonavir. The onset of rebound in COVID-19 symptoms along with evidence of SARS-CoV-2 infection must occur within 2 weeks (14 days) after completion of an initial 5-day course of nirmatrelvir/ritonavir.

Eligible participants for this study will be randomly assigned (2:1 allocation of active to placebo) to receive:

- nirmatrelvir plus ritonavir orally q12h for 5 days; or
- placebo plus ritonavir orally q12h for 5 days.

Randomization will be stratified by geographic region.

Participants will be screened within 24 hours before randomization.

Participants must be randomized within 48 hours from the onset of the rebound COVID-19 symptoms and must be randomized within 24 hours of a positive baseline rapid antigen test. The total study duration is up to 24 weeks, including study intervention administration through Day 5 or Day 6, efficacy and safety assessments through Day 34, and long-term follow up at Weeks 12 and 24.

Participants are eligible if they are at least 12 years of age (and weigh ≥ 40 kg at screening) and have at least 1 characteristic or underlying medical condition associated with an increased risk of developing severe illness from COVID-19. However, participants who are immunocompromised are excluded from this study as they may have prolonged viral shedding due to their immunocompromised state[14,15]. Participants will be eligible for enrollment irrespective of COVID-19 vaccination/boosted status (except for time course restrictions listed in the exclusion criteria).

An independent E-DMC will review unblinded data to ensure the safety of participants on an ongoing basis throughout the duration of the study.

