6.1.1. Administration

The first dose of study intervention will be administered at the site.

Nirmatrelvir 150 mg tablets or placebo for nirmatrelvir will be administered with ritonavir 100 mg for 5 days. Participants will be dispensed 1 blister wallet card of nirmatrelvir 150 mg tablets and 1 bottle of ritonavir capsules at the Day 1 site visit. Participants will be instructed to take:

- 2 tablets of nirmatrelvir 150 mg or placebo for nirmatrelvir q12h;
- 1 capsule of ritonavir 100 mg q12h.
 - Participants with moderate renal impairment (eGFR \geq 30 to $<$ 60 mL/min/1.73 m 2 [or eCrCl \geq 30 to $<$ 60 mL/min] at screening) will receive either 1 tablet of nirmatrelvir 150 mg and placebo for nirmatrelvir or 2 tablets of placebo for nirmatrelvir. The dose for ritonavir remains unchanged (ie, participants will receive 1 capsule of ritonavir 100 mg q12h).

Participants should take the first dose of study intervention on Day 1, during the in-person visit; that is, participants should take nirmatrelvir/placebo and ritonavir at the same time (no more than 15 minutes apart). The study intervention should be taken every 12 hours (\pm 4 hours), and not more than twice in a calendar day. Depending on the time of first dose, the timing of the second dose may be adjusted slightly to allow the participant/caregiver to select a convenient 12 hour dosing schedule as long as the next dose is taken at least 4 hours, but no later than 16 hours, after the first dose. Once the dosing schedule is adjusted, all subsequent doses should be taken every 12 hours (\pm 4 hours).

If a dose is delayed, it should be taken as soon as possible (but no later than 8 hours after the scheduled 12-hourly dose time), then resume the normal dosing schedule. If the participant misses a dose by more than 8 hours, the participant should not take the missed dose and instead take the next dose at the regularly scheduled time. The participant should not double the dose to make up for a missed dose. Dosing should be stopped at the end of the treatment period (Day 5 or 6). Any remaining tablets and/or capsules at the Day 5 visit should be returned. If the Day 5 visit is conducted prior to the last dose of study intervention (ie. Day 6), any remaining tablets or capsules should be collected at the next visit.

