8.1.3. Telehealth Visits

Telehealth visits may be used to assess participant safety and collect data points. Telehealth includes the exchange of healthcare information and services via telecommunication technologies (eg, audio, video, videoconferencing software) remotely, allowing the participant and the investigator to communicate on aspects of clinical care, including medical advice, reminders, education, and safety monitoring. The following assessments must be performed during a telehealth visit (see the [SoA](#)):

- Review and record study intervention(s), including compliance and missed doses.
- Review and record any AEs and SAEs since the last contact. Refer to [Section 8.4](#).
- Review and record any new concomitant medications or changes in concomitant medications since the last contact.
- Review and record contraceptive method and results of pregnancy testing. Confirm that the participant is adhering to the contraception method(s) required in the protocol. Refer to [Appendix 4](#).

Study participants must be reminded to promptly notify site staff about any change in their health status.

Observe (ie, video, videoconferencing software) the participant performing the rapid antigen test (participant self collected rapid antigen test), if the procedure is conducted remotely, and record the results for offsite visits in accordance with the [SoA](#).

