3.5.1. Adverse Events

An adverse event (AE) is any untoward medical occurrence in a study participant administered a product or medical device; the event need not necessarily have a causal relationship with the treatment or usage. An AE is considered a treatment-emergent adverse event (TEAE) if the event started on or after the study medication start date and time.

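### A Day 34 visit held early in its ±3-day window falls 25 to 27 days after the last dose, short of the protocol's 28-day minimum for AE and SAE collection

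*Protocol*

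**What the plan says.** - **Required period.** Protocol Section 8.4.1 starts active collection of AEs and SAEs at informed consent and continues it "through and including a minimum of 28 calendar days" after the last dose. The early endings it lists are screen failure and withdrawal of consent for further data collection. An early Day 34 visit is not among them.
- **Last dose.** Section 6.1.1 states: "Dosing should be stopped at the end of the treatment period (Day 5 or 6"). Table 1 explains the later day: "If only 1 dose of study intervention is administered on Day 1, study intervention should end on Day 6". Section 4.1 describes the study as "study intervention administration through Day 5 or Day 6, efficacy and safety assessments through Day 34".
- **Scheduled contacts.** Table 1 counts each "Day relative to start of study intervention (Day 1") and gives the Day 34 visit a window of ±3 days. The row "Serious and nonserious AE monitoring" is marked at every visit from Screening to Day 34 and at early termination. It is blank at Weeks 12 and 24, which are telemedicine visits.
- **Telehealth visits.** Section 8.1.3 lists, among the tasks for such a visit, "Review and record any AEs and SAEs since the last contact". It introduces that list by referring back to Table 1.
- **Analysis.** SAP Section 3.5.1 counts an AE as treatment-emergent "if the event started on or after the study medication start date and time". It sets no end date.

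**The concern.** The 28-day minimum is the protocol's own safety standard, and sites will work from Table 1 to deliver it. On the nominal day the schedule fits, and for a participant who finishes on Day 6 it fits with nothing to spare. Any visit before Day 34 therefore breaks the minimum for that participant, and the window allows three such days. A Day 6 finish is an expected path that Table 1 provides for.

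Incidence of TEAEs, and of SAEs and AEs leading to discontinuation, are secondary endpoints. Because the TEAE definition has no end date, the observation period is set by when participants are last asked. Those seen early, with no further contact, are asked about a slightly shorter period than the protocol promises.

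**Working it through.** **Inputs**

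- Minimum collection after the last dose: 28 days (Protocol 8.4.1)
- Last dose: Day 5 or Day 6 (Protocol 4.1, 6.1.1, Table 1)
- Day 34 window: 34 − 3 = Day 31 to 34 + 3 = Day 37 (Table 1). The viral RNA window in SAP Appendix 2.1 has the same limits.

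**Formula.** Days covered = study day of the visit − study day of the last dose. The minimum is reached on last-dose day + 28.

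**Nominal visit.** 34 − 5 = 29 and 34 − 6 = 28. Both meet the minimum.

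**Day on which the minimum is reached.** 5 + 28 = Day 33; 6 + 28 = Day 34.

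**Whole window**

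| Visit held on | Days after a Day 5 last dose | Days after a Day 6 last dose |
|---|---|---|
| Day 31 | 26 (short by 2) | 25 (short by 3) |
| Day 32 | 27 (short by 1) | 26 (short by 2) |
| Day 33 | 28 | 27 (short by 1) |
| Day 34 | 29 | 28 |
| Day 35 | 30 | 29 |
| Day 36 | 31 | 30 |
| Day 37 | 32 | 31 |

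Of the 7 permitted days, 2 fall short after a Day 5 last dose and 3 after a Day 6 last dose.

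**Early stoppers.** Last dose on Day 4: 31 − 4 = 27, so only a Day 31 visit is short. Last dose on Day 3: 31 − 3 = 28, so Day 3 or earlier is covered on every permitted day.

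**Next possible contact.** Taking Week 12 as Day 84 (an assumption) with its ±7-day window, the earliest date is 84 − 7 = Day 77. That is 77 − 31 = 46 days after a Day 31 visit.

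**Counting convention.** The table counts the day after the last dose as day 1. If the last-dose day itself were day 1, the minimum would end on 5 + 27 = Day 32 or 6 + 27 = Day 33. Day 31, or Days 31–32, would still fall short.

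**The case against.** The strongest reply is that the two provisions do not conflict. Section 8.4.1 sets a floor and the ±3 days is a scheduling tolerance. A site meets both by holding the visit later or by making one more contact. Section 8.4 ties AE questioning to the collection period, not to a numbered visit, and nothing says collection closes at the Day 34 visit. Participants remain in the study to Week 24, unplanned visits are allowed, and AEs may be assessed by telemedicine. Section 8.1.3 words its telehealth AE review as mandatory. Because the TEAE definition is open-ended, an event that starts after an early visit and is recorded later still counts.

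Much of this stands. The duty is not shortened, no figure in the plan is miscalculated, and a careful site can comply. What it does not show is that the schedule delivers the minimum:

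- Section 8.1 calls adherence to Table 1 essential, and a site can follow Table 1 exactly with no marked contact at or beyond 28 days.
- Unplanned visits are at the investigator's discretion.
- Section 8.1.3 sends the reader back to a table whose AE cells are blank at Weeks 12 and 24, so it is unclear whether the review applies there.
- If the review is done at Week 12, it relies on recall more than six weeks after a Day 31 visit. For late enrollees it may also miss the primary analysis, which Section 4.1 places once everyone has completed Day 34.

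**Conclusion.** The point holds, as a minor one. Table 1 does not guarantee the 28-day minimum for a participant who doses through Day 5 or Day 6 and is seen early in the Day 34 window. The largest shortfall is 2 days after a Day 5 last dose and 3 days after a Day 6 last dose. Safety observation falls below the minimum only if the site makes no further AE contact after the early visit.

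The number of participants affected cannot be estimated, because the documents say nothing about how many visits will be early. There is no reason to expect early visits to differ by arm, and the safety summaries are descriptive. The primary analysis, power and Type I error are untouched. The early termination visit was not assessed.

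**What to change.** Either of two changes is enough:

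1. **Change the Day 34 window to −0/+3 days.** This gives 34 − 5 = 29 to 37 − 5 = 32 days after a Day 5 last dose, and 34 − 6 = 28 to 37 − 6 = 31 days after a Day 6 last dose. A −1/+3 window would be enough only for participants who finish by Day 5.
2. **Keep ±3 days and add a note to the AE row of Table 1.** The note would require a documented telehealth AE/SAE query at least 28 days after the last dose for anyone whose Day 34 visit falls earlier.

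The first option cuts the permitted days from 7 to 4, and visits on Days 31–33 would become deviations. The second keeps the flexibility at the price of a short call for those seen early, a contact that Section 8.4.1 in effect already expects. Either needs a small protocol amendment, with the ethics approval that Section 10.1.1 requires, so it is best combined with the next planned amendment. The second option is less disruptive if recruitment is under way.
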